24 assessed at pre-treatment, post-treatment, and then 1- and 4-months after treatment completion.

25 3. OBJECTIVES/SPECIFIC AIMS/RESEARCH QUESTIONS

26 **Purpose:** The purpose of this randomized controlled trial (RCT) is to evaluate the efficacy of five 60-minute sessions
27 of Written Exposure Therapy for Suicide (WET-S) + Treatment as Usual (TAU) compared with TAU in high-risk,
28 suicidal service members, veterans, and DEERS eligible beneficiaries with posttraumatic stress disorder (PTSD) or
29 posttraumatic stress symptoms (PTSS).

30 42. Research Aims and Hypotheses:

31 Aim 1: Determine if Written Exposure Therapy for Suicide (WET-S) reduces the presence, frequency, and severity of
32 suicidal ideation, suicide plans, suicide gestures, suicide attempts, non-suicidal self-injurious behaviors, and re-
33 hospitalization for suicidality measured by the Self-Injurious Thoughts and Behaviors Interview (SITBI; Nock et al.,
34 2007) among service members, veterans, and DEERS eligible beneficiaries admitted to an acute psychiatric
35 inpatient unit for suicidal ideation (SI) and/or attempt with posttraumatic stress disorder (PTSD) or posttraumatic
36 stress symptoms (PTSS) compared with Treatment as Usual (TAU).

37 Hypothesis 1. Compared with TAU alone, WET-S + TAU will result in significantly greater reductions in
38 suicide-related outcomes pre-treatment to 1- and 4-months follow-up.

39 Aim 2: Determine if Written Exposure Therapy for Suicide (WET-S) reduces posttraumatic stress symptoms (PTSS)
40 severity measured by the Clinician Administered PTSD Scale for DSM-5 (CAPS-5; Weathers, Blake, Schnurr,
41 Kaloupek, Marx & Keane, 2013) among service members, veterans, and DEERS eligible beneficiaries admitted
42 to an acute psychiatric inpatient unit for suicidal ideation (SI) or attempt and posttraumatic stress disorder (PTSD) or
43 PTSS compared with Treatment as Usual (TAU.)

57 Hypothesis 2. Compared with TAU alone, WET-S + TAU will result in significantly greater reductions in
58 PTSS severity from pre- to post-treatment, 1- month, and 4-month follow-up.

59
60 Aim 3: Determine if reductions in posttraumatic stress symptoms (PTSS) severity mediate the association between
61 treatment condition and suicide-related outcomes (suicidal ideation, plans, gestures, attempts, non-suicidal self-
62 injurious behaviors, and re-hospitalizations) measured by the Clinician Administered PTSD Scale for DSM-5 (CAPS-

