7. RESEARCH PLAN

7.1 Selection of Subjects

- Target enrollment (number consented): 140
- Target number randomized: 124

7.1.1. Subject Population. Active duty military service members and veterans admitted to the CRDAMC inpatient psychiatry unit for treatment for suicidal thoughts or behaviors and PTS. The study will use a continuous enrollment process to allow for maximum flexibility in meeting individual patient/participant scheduling needs. Active duty service members will have priority for being enrolled in the study.

197

7.1.2. Source of Research Material. Interviews, self-report questionnaires, medical record review.

198

7.1.3. Inclusion and Exclusion Criteria.

Inclusion Criteria

1. Active duty military service member, veteran, or and DEERS eligible beneficiary (age 18- 65 years) hospitalized at Carl R Darnall Army Medical Center (CRDAMC) for non-suicidal self-injury, suicide thoughts, suicide plan or attempt confirmed by CRDAMC inpatient admission documentation.
2. PTSS of at least moderate severity (total scores > 20) confirmed by the CAPS-5.
3. Speak, read, and write English.

208

Exclusion Criteria

1. Active psychosis.
2. The presence of moderate to severe cognitive impairment (as determined by the inability to comprehend the baseline screening questionnaires).
3. The presence of any clinically significant factor that may impair an individual's ability to comprehend and effectively participate in the study, e. g., the presence of extreme agitation or violent behavior.

215

7.1.4. Description of the Recruitment and Prescreening Process. Under a waiver HIPAA Authorization for screening, study staff will collaborate with CRDAMC staff to identify potential participants who have been admitted for suicide thoughts and/or suicidal behaviors and that have symptoms of PTS as documented as part of the admission assessments.

220

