360 expectations in this yet unstudied population, we powered the study to detect small to medium sized effects for the group
361 by time interaction. Power was estimated using Repeated Measures and Sample Size computer software, accessible at
362 <https://rmass.org>. Assuming subject level randomization, a quadratic design matrix for the time effect, a 1-tailed alpha
363 level of .05, desired power of .80, equal sized treatment groups at baseline, an overall expected 15% attrition rate, a
364 stationary AR1 error correlation matrix starting at a modest $r = .30$, and desire to be able to detect at least a conventional
365 small to medium sized effect ($d = .35$) at the final assessment, the desired total sample size we intend to recruit is $N = 124$
366 ($n = 62/\text{group}$), a feasible recruitment goal given the targeted population.
367

368 **7.4.2 Primary (i.e., primary outcome variables) and secondary endpoints.** The primary dependent variables for suicidality
369 are the Self-Injurious Thoughts and Behaviors Interview (SITBI) interview and the Depression Symptom Index-Suicidality
370 Subscale (DSI-SS) self-report. The primary dependent variables for PTS symptoms and PTSD are the Clinician
371 Administered PTSD Scale (CAPS-5) interview and the PTSD CheckList-5 (PCL-5) self-report. Secondary endpoints
372 include associated psychopathology (severity scores on measures of depression, general anxiety, anger, and PTSD-
373 related cognitions)
374

375 **7.4.3 Data Analyses.** To examine hypothesis 1 (determine if WET-S + TAU reduces presence (past month), frequency,
376 and severity of suicidal ideation, suicide plans, suicide gestures, suicide attempts, and non-suicidal self-injurious
377 behaviors and re-hospitalizations related to suicidality relative to TAU only and hypothesis 2 (determine if WET-S + TAU

378 reduces PTS symptom severity relative to TAU only) , we will conduct intent-to-treatment (ITT) analyses including all
379 randomized participants who attend at least the first therapy session. General or Generalized Linear Mixed Effects
380 models, depending on the nature of the specific outcome, will be implemented for the primary ITT randomized
381 comparison of total CAPS-5 scores as well as SITBI variables of interest and number of subsequent inpatient
382 hospitalizations for suicidal behavior. The planned statistical design includes fixed effects for treatment (between-

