383 groups), time (within-subjects), and the group by time interaction. This latter effect captures differences in changes over
384 time between the groups; as such it is the effect of substantive interest in each of the models that will be examined.
385 Advantages of the general(ized) linear mixed effects model include the ability to include cases with missing data
386 (assumed missing at random), flexible specification of the covariance structure among the repeated measures, the ability
387 to model nonlinear trajectories of change over time, and the ability to perform between- and within-groups contrasts both
388 at and across assessments to examine significant group by time interactions. Prior to performing statistical analyses, the
389 data will be inspected to determine the advisability of scale transformation to normalize distributions (where applicable)
390 or reduce variance heterogeneity and to identify missing data, outliers, or other unusual features that may be influential.
391 To test hypothesis 3, growth curve modeling will be used to examine mediation. Specifically, treatment condition will be
392 entered as a predictor of change in both PTS symptom severity and suicide related outcomes. To achieve mediation,
393 WET-S +TAU would achieve superior reductions in suicide related outcomes and PTS symptom severity relative to TAU
394 only. Finally, we will examine the indirect effect of treatment condition on suicide related outcome change via PTSD
395 symptom change. Identification of an indirect effect would allow us to conclude that WET-S + TAU's superior effect on
396 suicide risk relative to TAU only is mediated by changes in PTS symptoms.
397

398 **7.7 Confidentiality.** All video telehealth therapy sessions and interview assessments will be conducted in private offices
399 in the CRDAMC acute inpatient psychiatry unit and then via video telehealth from a private location of the participant's
400 choosing once the participant is discharged from inpatient care. All assessment interviews and WET-S treatment
401 sessions speaking with the therapist will be recorded using an audio-recorder external to the HIPAA compliant telehealth
402 platform. Recordings will be labeled with the participant's study ID number.
403 The recordings will be uploaded to a secure password protected server immediately after the session is completed. The

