432 these interventions suggest participants typically experience decreased emotional distress immediately
433 afterwards.
- 434

436
437
438

- Possibility of becoming emotionally upset or experiencing an initial increase of PTSD symptoms due to the discussion or journaling of traumatic events.

439 **Rare and Serious (expected to occur in less than 5 out of 100 participants):**

440
441
442
443
444
445
446
447
448
449
450
451
452
453
454
455

- With the handling of medical and research records there is always the possibility of a breach of confidentiality. However, every effort is made to protect the privacy of participants. Every member of the research team is carefully trained and monitored about how to store, handle, and protect participant records.
- Assessment and therapy sessions that are conducted via video telehealth are subject to risks to confidentiality if others in the CRDAMC inpatient ward or home or other location can hear what is being said during the encounter. To minimize this risk, while in the inpatient ward participants will be placed in a private room while monitored by a CRDAMC staff member when doing study activities. When the patient is completing a video telehealth therapy session or assessment following discharge from the inpatient ward, participants will be encouraged to use headphones and to find a quiet area of the home to hold the encounter. Also, although video telehealth sessions are transmitted securely, there is always a risk that others (not affiliated with this research) could breach the network security systems and access the information. Ensuring that the participant has a virus protection on his or her computer will minimize this risk.
- It is possible that technical difficulties will result in missing a scheduled treatment session. The research team will work closely with participants to solve technical problems to minimize missed treatment time and also to re-schedule and conduct missed treatment sessions as soon as possible.

456 **Risks of Suicidality Thoughts and Behaviors or a PTSD Diagnosis regardless of Treatment.** One of the risks
457 of suicidality thoughts and behaviors as well as PTSD both in and out of treatment is attempted suicide, which can
458 result in death. Prior research has shown that, following a suicide attempt, up to half of patients in treatment make
459 another suicide attempt. If the suicide attempt occurs within the first year of treatment, on average a patient will

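### The Aim 1 models carry no baseline covariate, so the count of later hospitalizations is compared without regard to baseline risk; prespecifying index-admission type would be a cheap, modest gain

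*Combined protocol and SAP*

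**What the plan says.** Section 7.4.3 (Data Analyses) gives one specification for the Aim 1 and Aim 2 models: "The planned statistical design includes fixed effects for treatment (between" arms), continuing with "groups), time (within-subjects), and the group by time interaction". Of the interaction it says "as such it is the effect of substantive interest in each of the models that will be examined". No baseline covariate is named in that section. The outcomes are described as a "comparison of total CAPS-5 scores as well as SITBI variables of interest and number of subsequent inpatient" stays for suicidal behavior.

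Hypothesis 1 (section 3) concerns reductions in "suicide-related outcomes pre-treatment to 1- and 4-months follow-up". The baseline SITBI value is therefore one of the repeated responses. Hospitalizations are counted only after entry, and no matching baseline count is stated.

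Inclusion criterion 1 (section 7.1.3) admits people hospitalized "for non-suicidal self-injury, suicide thoughts, suicide plan or attempt confirmed by CRDAMC inpatient admission documentation". Section 7.1.2 lists medical record review as a data source. Section 15.0, item 5, has the SITBI answered over the whole lifetime, so attempt history is collected too.

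Section 8.1 (Risks) reports that "following a suicide attempt, up to half of patients in treatment make" a further attempt. It gives no rate for patients without an attempt.

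**The concern.** The trial pools people admitted after an attempt with people admitted for thoughts, a plan or self-injury. If the first group has more later events, two things follow when the model ignores it. A chance difference between arms in the share of attempters feeds into the estimated effect, and some power is given up.

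The hospitalization outcome is the most exposed, because no earlier response in its model stands in for baseline risk. For SITBI events, the baseline response carries part of this information, but not necessarily all of it.

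Timing matters too. A covariate added after an imbalance has been seen looks chosen to suit the result. The same covariate written into the plan beforehand does not.

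**Working it through.** **Inputs from the documents.** 62 per arm, 15% attrition (62 x 0.85 = 52.7 left), one-tailed alpha .05, target d = .35 (section 7.4.1); up to 50% re-attempting (section 8.1).

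**Assumed, because the documents do not give them.** Share admitted for an attempt, 20-50%; event risk 30-50% in attempters and 10-20% in the others; odds ratio for treatment; variance explained by the covariate.

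**The plan's own figure.** N = 124 cannot be confirmed. A plain final-visit comparison needs 2 x (1.645 + 0.842)^2 / 0.35^2 = 101 per arm. The number of visits and the effect profile entered in the software are not stated, so 124 is neither confirmed nor called wrong. Nothing below depends on it.

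**Chance imbalance.** The SD of the between-arm difference in attempter share is sqrt(2p(1-p)/62).
- p = 20%: 7.2 points. p = 40%: 8.8. p = 50%: 9.0.
- A gap of 10 points or more has probability 16-27% over p = 20-50%.
- At p = 40%, the 95% limit is 1.96 x 8.8 = 17.2 points. With risks of 50% v 10%, that shifts the arm difference by 17.2 x 0.40 = 6.9 points. With 30% v 10%, it is 17.2 x 0.20 = 3.4.
- A typical gap (mean absolute value about 7 points) shifts it by 7 x 0.40 = 2.8 points.
- For scale, d = .35 is a log odds ratio of .35 x pi/sqrt(3) = 0.635. That is 8.3 points from a 20% TAU rate. It is 10.3 points from the 26% that these inputs imply (.4 x .50 + .6 x .10).

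**Outcome with no baseline, continuous approximation.** Power = Phi(.35 x sqrt(52.7/2) / sqrt(1-R2) - 1.645). It is 0.560 unadjusted, and 0.579, 0.598 or 0.642 if the covariate explains 5%, 10% or 20% of the variance.

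**Binary follow-up event.** Logistic regression, 62 per arm, log odds ratio -1.1, 3000 runs:

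| Attempters | Risk, attempters v others | Unadjusted | Adjusted |
|---|---|---|---|
| 20% | 50% v 10% | 0.513 | 0.550 |
| 20% | 50% v 20% | 0.703 | 0.718 |
| 20% | 30% v 10% | 0.462 | 0.481 |
| 40% | 50% v 10% | 0.623 | 0.690 |
| 40% | 50% v 20% | 0.751 | 0.776 |
| 40% | 30% v 10% | 0.562 | 0.564 |

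Type I error was 0.043-0.056 unadjusted and 0.041-0.057 adjusted. In a count model the gain was only about 1 to 2 points.

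**Longitudinal models with baseline as a response.** A constant covariate effect cancels out of change. In the linear model (62 per arm, four visits, AR1 .30), adding the main effect left power for group by time identical (for example 0.457 v 0.457). A binary version (GEE, 53 per arm, 500 runs) gave .352 v .352, .346 v .342 and .358 v .360. Covariate by time changed linear-model power by -0.5 to +0.1 points for moderate effects. Power rose from 0.378 to 0.402 when the covariate shifted follow-up by 1 SD but not baseline.

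**Does the baseline response already do the job?** Suppose baseline past-month attempt coincides with attempt admission. A 17.2-point excess of attempters then adds 17.2 points at baseline but 6.9 at follow-up. On the risk-difference scale the change contrast moves by 6.9 - 17.2 = -10.3 points, which favors the arm with more attempters. Simulated power in that case (53 per arm, odds ratio 0.4, 50% v 10%, 3000 runs):

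| Attempters | Follow-up, unadjusted | Group by time | Follow-up, adjusted |
|---|---|---|---|
| 40% | 46% | 45% | 52% |
| 30% | 42% | 42% | 48% |

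**The case against.** The strongest reply is that covariate choice is largely discretionary. Randomization keeps the unadjusted test valid, and for SITBI attempts the past-month baseline response should already hold much of the admission information. Most of that stands: type I error is not at issue, and a main effect alone would leave the planned interaction test essentially unchanged. It does not reach the hospitalization count, which has no baseline response. Nor does it show that baseline as a response recovers the loss; in the last table above it did not.

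A second reply is that large gains need large inputs. This also stands. The 50% is an upper figure with no time window, and at 25-30% v 10% the gain is only about 1 to 2 points.

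A third is that randomization may have been stratified. The available text does not contain the randomization procedure, so this cannot be judged. If admission type is a stratum, it belongs in the model anyway.

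A reader might infer from section 8.1 that the protocol itself treats a prior attempt as a strong predictor. It does not: it reports one re-attempt rate, with no comparator, in a paragraph on risks. Criterion 1 also lists four reasons for admission, not attempt against ideation, and it uses the record to confirm eligibility. It does not say that the reason is stored as an analysis variable.

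**Conclusion.** The point holds as a modest improvement in efficiency and robustness, clearest for later hospitalizations. The models are unadjusted, the information can be obtained for every participant, and prespecified adjustment is legitimate. The gain is about 0 to 7 power points for a binary follow-up event and about 1 to 2 in a count model. It is near zero if admission type is weakly prognostic. These sizes rest on assumed attempter shares, event risks and odds ratios.

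Two stronger readings fail. One is that the planned analysis is biased or invalid; simulated type I error is near 5% with or without the covariate. The other is that chance imbalance could readily match the effect sought. Even at the 95% limit with 50% v 10% risks, the shift is 6.9 points against 8.3 or 10.3, and a typical shift is 2.8.

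**What to change.** Add to section 7.4.3, before unblinding:

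- Define index-admission type as attempt v no attempt, taken from the admission record and coded without knowledge of arm.
- Include it as a fixed covariate in the model for later hospitalizations.
- In the longitudinal SITBI event models, include it with a covariate-by-time term, which keeps group by time as the effect of interest. Alternatively, model follow-up visits only, with the covariate and the baseline value. State which one is used.
- Use this single covariate. Leaving lifetime attempt history out of the main model avoids a fallback that depends on how many events occur.
- Report a standardized risk or rate difference beside each adjusted ratio.

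The cost is a short SAP paragraph and one coded field from a record already reviewed. The hospitalization model gains one parameter. The longitudinal models gain the main effect plus one parameter per time term, which matters where events are sparse. The adjusted odds ratio is conditional on admission type, hence the standardized difference.

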112 SE = 0.07, p<.001), indicating that participants were significantly less likely to endorse SI over time. Roughly half of
113 those who endorsed SI at baseline no longer endorsed SI 60 weeks later.

115 To directly target suicidal risk and PTSD among service members admitted to an acute psychiatric inpatient unit the
 116 study will use a new formulation of WET referred to as WET-for suicide or WET-S that includes crisis response
 117 planning (CRP) for suicide prevention to the WET condition. CRP is a brief strategy that reduces suicide attempts
 118 among military personnel by 76% compared with typical suicide risk management strategies (Bryan et al., 2017a).
 119 CRP also contributes to significantly faster reductions in suicide ideation (Bryan et al., 2017a), as well as immediate
 120 reductions in emotional distress and suicidal intent (Bryan et al., 2017b). WET-S aims to work synergistically by
 121 addressing trauma-related symptoms or cognitive-affective states (e.g., intrusive thoughts, self-blame, hyperarousal)
 122 that are both PTSD treatment targets and warning signs for suicidal thoughts and behaviors (Bryan, 2016; Bryan,
 123 Grove, & Kimbrel, 2017). The development and review of CRP aims to support the regulation of these trauma-
 124 focused cognitive-affective states (among other patient warning signs) while the patient engages in trauma-focused
 125 treatment through the WET protocol.

126
 127 WET-S will be delivered in a condensed or “massed” treatment format, consisting of at least one WET-S session
 128 each day. For some patients, two WET-S sessions per day may be considered with the objective that the protocol
 129 is completed prior to discharge. Recent data support condensed formats version of evidenced-based cognitive
 130 behavioral therapies for PTSD work equally well as the spaced (weekly) version with significantly less dropout (Foa
 131 et al., 2018; Fredman et al., 2018; Peterson et al., 2018). Although primary data exist to support reductions in suicide
 132 risk with WET, it has yet to be tested with patients at high risk for suicide requiring inpatient hospitalization
 133 management. Therefore, as a part of risk management strategies for the experimental treatment of WET with this
 134 population we are including increased suicide risk monitoring and management by the inclusion of CRP in the WET
 135 condition (WET-S). WET-S will be delivered in five sessions, with the allowance of an additional two WET-S

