267 sessions will be provided to ensure the rationale of WET-S as a treatment for PTSD is understood by the participant
268 and to allow for a full course of WET-S sessions. WET-S will be delivered in a condensed or "massed" treatment
269 format, consisting of at least one WET-S session each day until the treatment is complete. For some participants,
270 two WET-S sessions per day may be considered to complete the protocol prior to discharge if possible. However, if
271 participants are discharged from inpatient care prior to completing the WET-S protocol, WET-S will continue using a
272 secure HIPAA-compliant video telehealth platform.
273

274
275 WET-S treatment also includes the development and monitoring of a Crisis Response Plan (CRP) for suicide risk.
276 Participants assigned to WET-S will complete the CRP prior to beginning their writing in session 1. Patient use of the
277 CRP since the previous session will be briefly reviewed at the start of each WET-S session to manage safety and
278 problem solve fluctuations in risk during treatment.
279

280 Treatment As Usual (TAU). The TAU condition consists of daily contact and patient centered care by the acute
281 psychiatric inpatient unit provider team (e.g., psychiatrists, therapists, case managers, behavioral health techs). TAU
282 includes initial psychiatric stabilization, nurse case management, medication management, psychoeducation groups,
283 and discharge planning. Patients engage with the provider team daily and have structured times for psychoeducation
284 groups, case management, medication management, hygiene, and meals.
285

286 **7.2 Drugs, Dietary Supplements, Biologics, or Devices.** N/A

320 All UTHSCSA STRONG STAR network connectivity is segmented with Access Control Lists and is not accessible to
321 any other UTHSCSA network segments. STRONG STAR data server is physically located at the Advanced Data
322 Center (ADC) has 24x7 onsite security, card key, biometric access controls and video surveillance. University of
323 Texas Health Science Center at San Antonio (UTHSCSA) ADC facility also maintains Gen 2 firewall devices to
324 protect and prohibit any unauthorized access to UTHSCSA data. All UTHSCSA network devices are monitored by
325 state-of-the-art monitoring applications that include configuration audit, management, and availability 24x7.
326

327 The UTHSCSA STRONG STAR data server is currently a VMware Instance running Windows Server 2016

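### Aim 3's rule would report PTS change as the mediator of the suicide-risk effect, but a reverse path or a shared cause can meet the same rule

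*Combined protocol and SAP*

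**What the plan says.** Section 7.4.3 tests hypothesis 3 by growth curve modelling, with treatment condition "entered as a predictor of change in both PTS symptom severity and suicide related outcomes". To count as mediation, "WET-S +TAU would achieve superior reductions in suicide related outcomes and PTS symptom severity relative to TAU" alone. The indirect effect through PTSD symptom change is then examined. The section closes with an unqualified inference: "Identification of an indirect effect would allow us to conclude that WET-S" + TAU's superior effect on "suicide risk relative to TAU only is mediated by changes in PTS symptoms".

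Mediation is otherwise mentioned only under Aim 3 and Hypothesis 3 in section 3, which name the CAPS-5 for PTS and the SITBI for suicide outcomes. None of these places states that the mediator is measured before the outcome, gives a reverse-order model, lists mediator-outcome confounders or plans a sensitivity analysis.

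The visible text of Figure 1 (section 6) shows self-report measures only at post-treatment, and interviews with self-report at 1 and 4 months.

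**The concern.** PTS change is not randomised. Randomisation supports the effect of WET-S on PTS and its total effect on suicide outcomes. It does not support the step from PTS change to suicidality change. Patients whose suicidality eases may report fewer PTS symptoms as a result, or something else that treatment moves may improve both. Either can produce superior reductions in both outcomes and a non-zero indirect effect, which is all the rule asks for.

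A shared cause is not far-fetched here. Section 7.1.8 says that "WET-S treatment also includes the development and monitoring of a Crisis Response Plan (CRP) for suicide risk", and section 5 credits that component with immediate "reductions in emotional distress and suicidal intent". Section 8.1 likewise says that earlier work with "these interventions suggest participants typically experience decreased emotional distress immediately" afterwards.

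At stake is the mechanism statement. Aim 3 is one of three stated aims, and the planned sentence could report a mechanism that the data cannot distinguish from its rivals.

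**Working it through.** The plan gives no power or error figure for hypothesis 3, so there is none to reproduce. The check is whether the rule separates mediation from its rivals.

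**Inputs from section 7.4.1.** d = .35, 62 per group, 15% attrition and a 1-tailed alpha of .05. Per arm: 62 × .85 = 52.7, taken as 53, or 106 in all. Section 7.4.3 gives no alpha for hypothesis 3, so applying the 1-tailed .05 to both group comparisons is an assumption.

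**Assumed.** A within-arm correlation r of .3 or .5 between the two changes, and d = .35 on both. The indirect effect counts as found if its 95% interval (or its 90% interval, matching 1-tailed .05) lies above zero. Change scores with ordinary least squares stand in for the growth model.

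**Three truths.** Let T be arm, M improvement in PTS and Y improvement in suicidality, each with within-arm SD 1 and normal errors.

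- Partial mediation: M = dT + e₁; Y = d(1 − r)T + rM + e₂.
- Reverse: Y = dT + e₁; M = d(1 − r)T + rY + e₂.
- Shared cause U, shifted by d/√r on treatment: M = √r·U + e₁; Y = √r·U + e₂, with no path between M and Y.

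In each, both group differences equal d and the within-arm correlation is r. The joint distribution of (T, M, Y) is therefore the same. The estimated indirect effect is a × b = d × r, that is .35 × .3 = .105 or .35 × .5 = .175. It is a share r (30% or 50%) of the total effect. In the second and third truths the real share passing through PTS is zero.

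**How often the rule is met** (20,000 simulated trials per cell):

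| Truth | r = .3, 95% / 90% interval | r = .5, 95% / 90% interval |
|---|---|---|
| Partial mediation | 24.4% / 32.6% | 32.8% / 39.3% |
| Reverse | 24.6% / 32.3% | 33.0% / 39.8% |
| Shared cause | 24.6% / 32.5% | 32.6% / 39.4% |

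A separate rerun with 6,000 trials per cell agreed to within about one percentage point.

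**If one change acts wholly through the other** (r = .4 to .6), the distributions are no longer identical, but the rule still does not separate them. With a 95% interval it is met in 9–17% of trials for the reverse path and 12–21% for true mediation. With a 90% interval both are 14–24%.

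**If there is no within-arm link**, the rule is met in 0.5% of trials (95% interval) or 1.3% (90% interval) at d = .35 on both changes. With a 90% interval this rises to about 3% at d = .5 and about 5% at d = .8 on both.

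**Timing.** Hypothesis 2 lists PTS severity at post-treatment and Hypothesis 1 lists suicide outcomes only at 1 and 4 months, which suggests a possible order. But the CAPS-5 and SITBI are interviews, and the visible Figure 1 text shows none at post-treatment. After baseline the two named Aim 3 measures therefore appear only at the same visits. Part of the schedule text is not visible, so this cannot be settled fully.

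**The case against.** **The limit is general.** Almost any trial with a non-randomised mediator shares it, and it can be handled when results are reported. That is true, and it is why the remedy is small. But this plan commits in advance to an unqualified conclusion.

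**Shared-cause evidence.** Section 5 says WET-S addresses states "that are both PTSD treatment targets and warning signs for suicidal thoughts and behaviors", which a reader might take as the protocol naming a shared cause. Its examples (intrusive thoughts, self-blame, hyperarousal) are largely PTS content, so the sentence mostly gives the rationale for the proposed mediator. The distress statements remain, but neither says that the fall in distress drives PTS change at 1 or 4 months. The documents make a shared cause plausible; they do not show one.

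**Crisis response planning.** A reader might infer that a direct effect of this planning on suicidality is enough to create false mediation. It is not: without a within-arm link between the two changes, the indirect effect is seldom found.

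**The simulation.** Equal rates follow from how the three truths were set up, so it adds scale to a logical point and proves nothing further. The rates move with the assumptions. For a shared cause at r = .5, a separate run with a 1-sided joint test gave 48% at d = .35 with 124 patients, and 71–72% at d = .5 with 106. No single rate describes this trial.

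**Sensitivity analysis.** In a linear change-score model, the residual correlation that brings the indirect effect to zero is simply the observed within-arm correlation, and it is imprecise here. With 106 patients, adjusting for arm, the Fisher half-width is 1.96/√102 = .194 on the z scale. An observed .30 then has a 95% interval of about .11 to .46, and .50 about .34 to .63. The quantity is also undefined as it stands for yes/no and count outcomes. This objection holds, so that analysis should be optional.

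**Conclusion.** The Aim 3 conclusion is wrong as written. Meeting the rule shows that treatment moved both outcomes and that the two changes go together within arms. It does not show that PTS change produced the change in suicidality. This rests on the text of section 7.4.3 and on the equivalence of the three models, not on any simulated rate.

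The 25% to 33% figures should not be read as the plan's false-positive rate. They are conditional on a rival explanation being true and on assumed correlations, with a simplified model. Nor do the documents support reading this as a fault in Aims 1 and 2, in the choice of a growth model, or as proof that no ordered analysis is possible.

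The change should be made, but it concerns the interpretation of one aim, not the randomised comparisons.

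**What to change.** 1. Replace the closing conclusion for hypothesis 3 with: *would be consistent with mediation by PTS change; reverse and shared causes cannot be excluded.*
2. Keep the planned growth model and report the reverse-order model (suicidality change to PTS change) beside it, labelled as a display of ambiguity and not a test of direction.

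Optional and supportive only:

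- For continuous outcomes, a sensitivity analysis for mediator-outcome confounding with its interval, stating that it shows how strong confounding would need to be, not whether it exists.
- A lagged model on the self-report measures (PCL-5 and DSI-SS), if the schedule allows. Section 15.0 mentions interim assessments for both. The visits and measures should be named in advance, and the text should say that a lag does not remove a shared cause.

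The cost is one sentence and a little extra analysis, with no new data. The downside is a more cautious Aim 3 conclusion.
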